The incidence of psychological comorbidities in paediatric and young adults with inflammatory bowel disease, and the impacts of mental health conditions on quality of life, disease severity and resource utilisation: a population-based cohort study in the UK

Protocol

NCT number: NCT05206734

Study ID: P043

Document Date: 24th January, 2022

Project highlights

- This study will provide the first UK-based population level analysis of the risk of psychological comorbidities in children, adolescents, and young adults with IBD. The data resulting from this project will provide a measure of the magnitude of any associations. These insights will be valuable for clinicians managing people IBD in this age range; allowing early interventions to be targeted to those most at risk, and potentially reducing the likelihood of more serious future mental health problems.
- The dataset available for use in this project is one of the highest quality primary care data sources available world-wide. It provides the complete coded primary care record with robust data on comorbidities and treatments. In the paediatric population complete records since birth are available for the majority of people.

- Our in-house matching algorithm ensures a higher quality of case-control matching than is available using any other existing statistical software or tools. This is vital to produce reliable data and satisfy external peer review. Matching within a population-based sample has additional advantages over the use of secondary care cohorts, US claim-based datasets, or disease registry datasets. These advantages include minimisation of bias in the control group and the opportunity to select a comparator group affected by another chronic condition.

Background

Inflammatory bowel disease (IBD) comprises 3 main subtypes; ulcerative colitis (UC), Crohn's disease (CD) and IBD unclassified (IBDU). IBD develops at any age; with around 10% diagnosed in childhood.(1) Whilst UC is the most common subtype of IBD in adults, CD is more common in the paediatric IBD (PIBD) population. International trends have confirmed a global rise in the incidence of PIBD; in particular, a steep rise in the incidence of CD.(2) In Scotland, data shows a dramatic increase in PIBD, especially in incidence of CD which has risen 500% over just 40 years.(3)

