PIBD is associated with more extensive disease compared to adult onset IBD, with additional considerations which include growth failure, delayed puberty, poor bone density and psychosocial impact during a vulnerable period of life.(1, 4) The goals of treating IBD are to induce and maintain remission and to avoid disease complications, drug-related complications and unnecessary surgery, psychological health, promoting a return to, and maintenance of, a normal lifestyle that includes education, family, social function and physical activity.(1, 5) Other essential goals in children include optimizing growth, puberty, and psychological health and promoting a return to, and maintenance of, a normal lifestyle that includes education, family, social function, and physical activity.(1)

Psychological comorbidities associated with PIBD include anxiety; which may be related to the perceived or actual side effects of IBD therapies, altered body image and a feeling of lack of control over their lives, and depression; associated with severe/active disease, current steroid use and the need for an ostomy.(6) Conflicting results and methodological constraints have limited previous understanding of psychosocial functioning in PIBD.(7) Reported rates of clinically significant symptoms of depression and anxiety have ranged from 25% to 73% in children and adolescents with PIBD.(6) However, recent studies highlight growing concerns for psychiatric morbidity in IBD in children and young adults. A US study(8) of 58,020 IBD patients aged 5-24 reported a prevalence of psychiatric disorders of 21.6%; mainly comprising depression and anxiety disorders. IBD was found to be 5 times more likely associated with psychiatric disorders than with controls, and the incidence of these disorders was associated with a steady increase in trend over time (2% in 2006 compared to 15% in 2017).(8) Similarly, Swedish data(9) from 6464 PIBD patients, indicate an association of IBD with psychiatric morbidity of 17.3%. Most concerningly, this study reported IBD to be significantly associated with suicide attempt and as well as mood disorders, anxiety disorders, eating disorders, personality disorders, attention-deficit/hyperactivity disorder, and autism spectrum disorders. Results for each sex were similar. A correlation of age and development of psychiatric disorders was indicated for patients with very early-onset IBD (<6 years).

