Furthering our understanding of the psychosocial sequelae of IBD in children and young adults is particularly important in light of evidence suggesting that symptoms of anxiety and depression may decrease adherence to treatment, thus impacting on longer term disease outcomes,(6) and has been emphasized in a recent call to action issued within gastroenterology to improve understanding and early identification of comorbidities associated with IBD.(10)

To the best of our knowledge, there have not been any large population-based studies assessing the association between psychosocial comorbidities in IBD in

children and young adults and disease related outcomes. The aim of this study is therefore to fill this data gap, and to examine the following objectives.

Such new insights will be valuable for clinicians in optimising patient care for IBD patients; allowing early interventions to be targeted to those most at risk, and potentially preventing the development of more serious mental health problems such as depression; linked to difficulties with medication adherence, and anxiety; which may exacerbate future disease activity.(7, 10)

Ultimately, we anticipate that these data will be useful in understanding the potential cycle and interrelationship between IBD and mental health in children and young adults.

Objectives: Stream 1 – Incidence of mental health conditions

Primary Objectives

- Compare the risk and cumulative incidence of mental health conditions in children and young adults with IBD compared to matched population controls in the primary care setting, stratified by IBD type

Secondary Objectives

- Determine severity of mental health conditions in those with and without IBD (e.g. evidence of self-harm, suicide attempt, behavioural disorders)

Objectives: Stream 2 – Impacts of mental health conditions

Primary Objective:

- Determine the association of mental health conditions in children and young adults with IBD on quality-of-life indicators

Secondary Objectives:

- Compare IBD severity/disease markers in children and young adults with IBD with and without mental health illness

- Compare healthcare resource utilisation in children and young adults with IBD with and without mental health illness

Methods

The study protocol was specified a priori and registered with ClinicalTrials.gov (Study identifier: NCT05206734).

Data source

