To evaluate the magnitude of potential bias from including, as matched controls, people who are registered with GP practices but who do not attend their practice, we also repeated the primary analysis including only controls with a least one primary care consultation in the year preceding their index date.

All statistical analyses were performed using R statistical package software version 3.4.1. The study was conducted in line with the RECORD (Reporting of studies conducted using observational routinely collected data) guidelines.(13)

Stream 2:

Stream 2: Study design

The proposed study will use the retrospectively collected data of all eligible patients within the database at the date of data extraction. Within this primary care cohort, all patients with IBD will be identified using diagnostic codes and prescription records. A diagnostic algorithm will be developed to facilitate robust case identification of IBD and IBD subtypes as well as mental health outcomes.

Stream 2: Study cohort

The eligible IBD cases will comprise all prevalent cases of IBD aged under 25 at 01/01/2015 (index date) comprising of the three main subtypes; ulcerative colitis (UC), Crohn's disease (CD) and IBD unclassified (IBDU), excluding microscopic colitis, radiation induced enterocolitis and drug-induced enterocolitis. We will extract sociodemographic details for all individuals. Sociodemographic data will comprise by age group, age at diagnosis, sex, ethnicity, and socioeconomic status. Ethnicity will be categorised as follows to be consistent with the UK official census categories: White, Asian, Black African/Caribbean, Mixed, and Other. The index of multiple deprivation (IMD) will be used as a measure of socioeconomic status. This is derived from patient postcode at the point of data extraction.

We will identify comorbid psychological condition groups in all people with PIBD. These will comprise 3 composite phenotypes; anxiety/panic disorders, major depression or depressive episodes, and other psychological conditions. Other psychological conditions will be a composite of; eating disorders, body image disorder, attention-deficit disorder (ADHD), behavioural disorders, adjustment disorder, acute stress disorder, schizophrenia, bipolar disorder and post-traumatic stress disorder (PTSD). Where numbers are sufficient, subgroups of the broad 'other psychological conditions' composite may be examined.

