We will use standard descriptive statistics (mean, standard deviations, etc) to describe the characteristics of the study cohort overall and by mental health phenotype. Across mental health condition phenotypes we will describe the incidence of recording of all the quality-of-life indicators, IBD severity markers, and healthcare resource utilisation outcomes up to five years after the index date (01/01/2015), compared to incidence in the group without mental health conditions. The end of follow-up will be the first of; 01/01/2020 (5 years after the index date) we will not follow patients up into 2020/21 due to changes in patient health behaviour and primary care interactions due to COVID-19, the patient's 25th birthday, date of loss to follow-up (either deregistration or death). All individuals contributing at least six months of follow-up time in the analysis will be included. We will not follow patients up into 2020/21 due to changes in patient health behaviour and primary care interactions due to COVID-19.

Relative incidence between those with and without mental health conditions will be estimated for repeated events (e.g. number of hospital admissions) and binary events (e.g. quality of life indicators) using, as appropriate, Poisson regression, negative binomial regression (if we need to account for overdispersion), or zero-inflated Poisson regression (if we need to model rare events). To account for variable duration of follow-up, we will include the natural logarithm of person-years of follow-up as a model offset. Confidence intervals will be estimated using robust SEs. Models will be adjusted for age, gender, socioeconomic status, ethnicity, and other childhood conditions (asthma, atopic dermatitis, allergic rhinitis, thyroid disease, epilepsy, diabetes, cancer, juvenile idiopathic arthritis (JIA) including systemic JIA, systemic lupus erythematosus (lupus), ankylosing spondylitis (AS) and psoriatic arthritis). Statistical significance for analyses will be reported using P values and 95% confidence intervals as appropriate.

Where numbers allow, we will report absolute and relative incidence in subgroups by, mental health condition group, age group (5-<12; 12-<16; 16-<18; 18-<25) (child, adolescent, young adult), and sex.

References

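### Stream 2 models adjust for no IBD characteristic, so a higher later rate of IBD severity markers in the depression group may partly reflect worse IBD already present at the index date

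*Combined protocol and SAP*

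**What the plan says.** The combined protocol and SAP enrols prevalent IBD cases aged under 25 at 01/01/2015 (Stream 2: Study cohort). It groups them by mental health status at that date, using "3 composite phenotypes; anxiety/panic disorders, major depression or depressive episodes, and other psychological conditions", plus a comparator group without mental health comorbidity, and follows them for up to five years.

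Stream 2: Statistical methods gives the covariates: "Models will be adjusted for age, gender, socioeconomic status, ethnicity, and other childhood conditions". A bracketed list of 11 conditions follows, from asthma to psoriatic arthritis. With the four demographic items, that makes 15 named covariates.

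Stream 2: Study outcomes lists IBD severity indicators that include oral steroids, any abdominal surgery, and stoma formation as a separate outcome. The matching objective is secondary: "Compare IBD severity/disease markers in children and young adults with IBD with and without mental health illness". The primary Stream 2 objective concerns quality-of-life indicators, which include IBD symptoms.

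The Background describes "depression; associated with severe/active disease, current steroid use and the need for an ostomy". It also says that "symptoms of anxiety and depression may decrease adherence to treatment, thus impacting on longer term disease outcomes".

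On baseline description, Stream 2: Study cohort states: "Sociodemographic data will comprise by age group, age at diagnosis, sex, ethnicity, and socioeconomic status". Sociodemographic characteristics are to be compared between the groups, and Stream 2: Statistical methods describes cohort characteristics by phenotype.

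**The concern.** A prevalent cohort taken on a fixed date mixes patients with different IBD types, durations and past severity. By the protocol's own account, depression goes with more severe disease, steroid use and ostomy. The same kinds of marker are then counted as outcomes after the index date, and no baseline version of them is in the model. Nothing else in Stream 2 fills the gap: the subgroups are mental health group, age group and sex; stratification by IBD type is stated only for Stream 1; the one sensitivity analysis concerns Stream 1 controls; and there is no rule for an outcome already present at index.

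What is at stake is interpretation. The title promises "the impacts of mental health conditions on quality of life, disease severity and resource utilisation", and the Stream 2 heading repeats the word 'impacts'. A rate ratio above 1 for steroids, surgery or stoma could be read as an effect of depression on the course of IBD. The planned model cannot separate that from more severe IBD at the outset.

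**Working it through.** The documents give no Stream 2 sample size, event rate or severity figure, so there is no plan figure to reproduce. The check has two parts.

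**1. Is any IBD characteristic in the model?** Age, gender, socioeconomic status and ethnicity make 4. The conditions are asthma, atopic dermatitis, allergic rhinitis, thyroid disease, epilepsy, diabetes, cancer, JIA, lupus, ankylosing spondylitis and psoriatic arthritis, which make 11. 4 + 11 = 15, and none is IBD type, age at or time since diagnosis, or prior IBD treatment or surgery. The joint conditions may overlap with IBD-related arthritis, but they do not measure bowel disease severity.

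**2. How far could an omitted severity factor move the result?** Take one binary factor, severe IBD at index, and no true effect of mental illness. Then

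apparent rate ratio = [1 + p1(k − 1)] / [1 + p0(k − 1)],

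where p0 and p1 are the shares with severe IBD among comparators and among those with mental illness, and k is the rate ratio of the later outcome for severe versus other IBD. Every input is an assumption.

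| p0 | p1 | k | Calculation | Apparent rate ratio |
|---|---|---|---|---|
| 0.30 | 0.20 | 4 | 1.60/1.90 | 0.84 |
| 0.30 | 0.20 | 3 | 1.40/1.60 | 0.875 |
| 0.25 | 0.25 | any | equal | 1.00 |
| 0.25 | 0.30 | 2 | 1.30/1.25 | 1.04 |
| 0.20 | 0.30 | 1.5 | 1.15/1.10 | 1.05 |
| 0.25 | 0.40 | 3 | 1.80/1.50 | 1.20 |
| 0.20 | 0.40 | 3 | 1.80/1.40 | 1.29 |
| 0.20 | 0.50 | 4 | 2.50/1.60 | 1.56 |

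A simulated Poisson model with a log person-years offset (400,000 patients, 15% depressed, follow-up 0.5 to 5 years, the 20% v 40%, k = 3 case) gave 1.29 without severity and 1.00 with it.

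**Imperfect marker.** A primary care marker will misclassify severity. Assume 70% sensitivity, 90% specificity and 30% of the cohort with mental illness. In large samples, adjusting for the marker moves 0.875 to 0.92, 1.20 to 1.12 and 1.56 to 1.33. It helps but is incomplete.

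**Over-adjustment.** Suppose instead that mental illness itself caused the 25% v 40% difference, with k = 3 and no other effect. Then 1.20 is a real total effect, and full adjustment for severity would return 1.00.

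**The case against.** The strongest reply is that the objectives are worded as association and comparison and the methods speak of describing relative incidence. On that wording the planned estimates are valid descriptions, and the causal reading rests mainly on 'impacts' in the title and heading. This stands, and it is why a change of wording is an acceptable fallback.

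A second reply is that severity at index may lie on the pathway, because mental illness may precede index and lower adherence. This also stands. It argues against making severity adjustment the sole analysis. It has much less force against adding IBD type and age at diagnosis.

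A third is that the plan does not ignore IBD features at baseline: age at diagnosis is extracted and falls under the planned group comparison, and characteristics are described by phenotype. That is correct, but IBD type and pre-index severity are not named in either comparison, and describing an imbalance does not adjust for it.

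A reader might infer more than the documents support in two ways:
- That Stream 2 results will be inflated. The documents give no severity figures by group, and the same formula gives ratios below 1, equal to 1 or trivially above 1 under other assumptions. The upper value needs severe disease 2.5 times as common (50% v 20%) and a severity rate ratio of 4.
- That the whole of Stream 2, including its primary objective, is compromised. The documented link concerns depression and bears most directly on steroids, surgery and stoma. For the anxiety/panic and 'other' phenotypes, and for outcomes such as school absence, unemployment, substance abuse and sleep problems, confounding by IBD severity is plausible but not documented.

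**Conclusion.** The point holds in a limited form and should be addressed before analysis. The omission of IBD type, age at or time since diagnosis, and pre-index severity is certain from the text. That it can confound the depression comparison follows from the protocol's own Background and outcome list. Whether it does, in which direction and by how much cannot be known until severity is tabulated by group. The illustrative range of 0.84 to 1.56, with mild cases at 1.04 to 1.05, rests wholly on assumed inputs, one binary severity factor and no true effect. It shows what is possible, not that bias is present. The main exposure is the secondary objective on IBD severity markers, with IBD symptoms in the primary objective plausibly affected.

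**What to change.** 1. Add IBD type (UC, CD, IBDU) and age at diagnosis or time since diagnosis to the planned Stream 2 models. Both are already to be obtained: subtype from the case algorithm, age at diagnosis by extraction.
2. Tabulate IBD type and pre-index severity by mental health group.
3. Beside the main model, report one severity-adjusted model with a single window for all patients: oral steroid prescriptions in the 12 months before 01/01/2015, and any prior abdominal surgery or stoma, restricted to patients with 12 months of look-back. State that this model may remove part of a real effect, because mental illness may precede index and reduce adherence. State also that residual confounding remains, since the protocol expects that biologics may be poorly captured in primary care.
4. If the severity-adjusted model is not added, replace 'impacts' with 'associations' in the title and Stream 2 heading and state the limitation.

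The cost is low: protocol wording and a few derived variables. Medication and surgery code lists are needed for the outcomes in any case, although sTable 3.2 so far shows headings only. The downsides are some loss of precision for sparse outcomes (15 covariates are already named and no event counts are given) and possible over-adjustment, which is confined to the second model.

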
Appendices

Appendix 1

sTable 1.1. Read and SNOMED codes to be used to identify cases of IBD and IBD subtypes

Ulcerative Colitis (UC)		
Read V2 Code	Term ID	Description
J41..	All	Ulcerative colitis and/or proctitis
J410.	All	Ulcerative proctocolitis
J4100	All	Ulcerative ileocolitis
J4101	All	Ulcerative colitis
J4102	All	Ulcerative rectosigmoiditis
J4103	All	Ulcerative proctitis
J4104	All	Exacerbation of ulcerative colitis
J410z	All	Ulcerative proctocolitis NOS
J411.	All	Ulcerative (chronic) enterocolitis
J412.	All	Ulcerative (chronic) ileocolitis
J413.	All	Ulcerative pancolitis
N0454	All	Juvenile arthritis in ulcerative colitis
N0310	All	Arthropathy in ulcerative colitis
Read CTV3 Code	Term ID	Description
XE0ag	All	Ulcerative colitis
XaZ2j	All	Left sided ulcerative colitis
XaYzX	All	Ulcerative pancolitis

XaK6E	All	Exacerbation of ulcerative colitis
J410.	All	Ulcerative proctocolitis
J4100	All	Ulcerative ileocolitis
J410z	All	Ulcerative proctocolitis NOS
J4103	Y30D7	Ulcerative proctitis
Jyu41	All	[X]Other ulcerative colitis
SNOMED Code	Term ID	Description
13470001		Chronic ulcerative ileocolitis (disorder)
14311001		Severe chronic ulcerative colitis (disorder)
15342002		Chronic ulcerative enterocolitis (disorder)
24829000		Eosinophilic ulcerative colitis (disorder)
43752006		Ulcerative colitis and/or proctitis
52231000		Chronic ulcerative proctitis (disorder)
52506002		Chronic ulcerative rectosigmoiditis (disorder)
64766004		Ulcerative colitis (disorder)
78324009		Mild chronic ulcerative colitis (disorder)
78712000		Moderate chronic ulcerative colitis (disorder)
128600008		Acute ulcerative colitis (disorder)
155764007		Ulcerative colitis
196986004		Ulcerative proctocolitis
196987008		Ulcerative ileocolitis
196988003		Ulcerative colitis
196989006		Ulcerative proctocolitis
196990002		Ulcerative proctocolitis NOS
196991003		Ulcerative enterocolitis
196992005		Ulcerative ileocolitis
197535008		[X]Other ulcerative colitis
201727001		Arthropathy in ulcerative colitis (disorder)

201807008		Juvenile arthritis in ulcerative colitis (disorder)
235714007		Ulcerative enterocolitis (disorder)
266447004		Ulcerative colitis
275549008		History of ulcerative colitis (situation)
295046003		Ulcerative proctocolitis (disorder)

J4000	All	Regional enteritis of the duodenum
J4001	All	Regional enteritis of the jejunum
J4002	All	Crohn's disease of the terminal ileum
J4003	All	Crohn's disease of the ileum unspecified
J4004	All	Crohn's disease of the ileum NOS
J4005	All	Exacerbation of Crohn's disease of small intestine
J400z	All	Crohn's disease of the small bowel NOS
J4010	All	Regional enteritis of the colon
J4011	All	Regional enteritis of the rectum
J4012	All	Exacerbation of Crohn's disease of large intestine
J401z	All	Crohn's disease of the large bowel NOS
J40z..	All	Crohn's disease NOS
Read CTV3 Code	Term ID	Description

SNOMED Code	Term ID	Description
3815005		Crohn's disease of rectum (disorder)
7620006		Crohn's disease of large bowel (disorder)
34000006		Crohn's disease (disorder)
38106008		Crohn's disease of ileum (disorder)
50440006		Crohn's disease of colon (disorder)
56287005		Crohn's disease of duodenum (disorder)
56689002		Crohn's disease of small intestine (disorder)
61424003		Crohn's disease of pylorus (disorder)
XE2QL	All	Crohn's disease
Xa0lh	All	Regional enteritis
X302r	All	Crohn's jejunitis
X302t	All	Crohn's ileitis
J4003	All	Crohn's disease of the ileum unspecified
J4004	All	Crohn's disease of the ileum NOS
J4002	All	Crohn's disease of terminal ileum
J400.	All	Regional enteritis of small bowel
XaK6C	All	Exacerbation of Crohn's disease of small intestine
J400z	All	Crohn's disease of the small bowel NOS
J401.	All	Regional enteritis of the large bowel
XE0af	All	Crohn's disease of the large bowel NOS
XaK6D	All	Exacerbation of Crohn's disease of large intestine
J40z.	All	Regional enteritis NOS
J4010	All	Crohn's colitis
J4011	All	Crohn's proctitis
X3050	All	Perianal Crohn's disease
J4001	Y30Fy	Regional enteritis of the jejunum
Jyu40	All	[X]Other Crohn's disease

70622003		Crohn's disease of pyloric antrum (disorder)
71833008		Crohn's disease of small AND large intestines (disorder)
91390005		Crohn's disease of jejunum (disorder)
155761004		Regional enteritis of small bowel
155762006		Regional enteritis of the large bowel
155763001		Regional enteritis NOS
196578009		Crohn's disease of oral soft tissues (disorder)
196975001		Regional enteritis - Crohn's disease
196976000		Regional enteritis of the jejunum
196977009		Crohn's disease of terminal ileum (disorder)
196978004		Crohn's disease of the ileum unspecified
196979007		Crohn's disease of the ileum NOS
196980005		Crohn's disease of the small bowel NOS
196981009		Regional enteritis of the large bowel
